4.2 Exclusion Criteria

- **4.2.1** Clinical or radiographic evidence of current brain metastasis. History of treated brain metastases is allowable.
- **4.2.2** Cardiac disease defined by:
 - a) Congestive heart failure > class II New York Heart Association (NYHA), or

b) Unstable angina (anginal symptoms at rest), or new-onset angina (began within the last 12 months), or myocardial infarction within the 12 months prior to registration, or

- c) Cardiac ventricular arrhythmias requiring anti-arrhythmic therapy or
- d) Atrial fibrillation or atrioventricular heart block
- **4.2.3** Uncontrolled hypertension (defined as persistent elevation of systolic blood pressure >150 mmHg or diastolic pressure > 100 mmHg; if screening BP measurement exceeds these parameters, BP measurement must be repeated at least one day later during the screening period; if repeat BP measurement exceeds these parameters, the subject should be excluded; if repeat measurement does not exceed these parameters, the subject is not excluded.)
- **4.2.4** Any (including pulmonary) hemorrhage/bleeding event Grade 3 or greater by National Cancer Institute Common Terminology Criteria for Adverse Events (NCI-CTCAE) V5 within 28 days prior to C1D1.
- **4.2.5** Major surgery, open biopsy, or significant traumatic injury within 42 days prior to C1D1.
- **4.2.6** Current serious, nonhealing wound, ulcer, or bone fracture within 42 days prior to C1D1.
- **4.2.7** History of abdominal fistula, gastrointestinal perforation, or intra-abdominal abscess within 6 months prior to C1D1.
- **4.2.8** Presence of an uncontrolled infection or infection that required IV antibiotics, antifungals, or antivirals within 14 days of C1D1.
- **4.2.9** Known human immunodeficiency virus (HIV) infection. HIV-infected subjects on effective anti-retroviral therapy are eligible if the most recent viral load test performed within six

months of screening (based on medical chart review) is negative. The safety of telatinib in this subject population has not been studied.

- 4.2.10 Known chronic hepatitis B, unless receiving antiviral treatment.
- 4.2.11 Known Child-Pugh Score B or C liver cirrhosis.
- 4.2.12 Diagnosis of immunodeficiency or is receiving systemic steroid therapy or any other form of immunosuppressive therapy within 7 days prior to the first dose of study treatment or has been diagnosed with an autoimmune disease that has required systemic treatment in the past 2 years (i.e., with use of disease modifying agents, corticosteroids, or immunosuppressive drugs). Patients that require replacement therapy (e.g., thyroxine [T4], insulin, or physiologic corticosteroid replacement therapy for adrenal or pituitary insufficiency, etc.) may be enrolled.
- **4.2.13** History of (non-infectious) pneumonitis that required steroids, or current pneumonitis, or has a history of interstitial lung disease.
- 4.2.14 Has received a live-virus vaccination within 30 days of planned treatment start.
- **4.2.15** Known history of proteinuria > 1gr/24 hours.
- **4.2.16** Previous or concurrent cancer that is distinct in primary site or histology from the current stomach or liver cancer. Subjects with cervical cancer in-situ, treated basal cell carcinoma, superficial bladder tumors (Ta and Tis) or any cancer curatively treated are not excluded.
- **4.2.17** Anti-cancer therapy (chemotherapy, hormonal therapy, radiation therapy, surgery, immunotherapy, biologic therapy, or tumor embolization) or investigational agent within 28 days prior to C1D1.
- **4.2.18** Known or suspected allergy to any component of telatinib or Keytruda
- **4.2.19** Prior or current history of substance abuse, or medical, psychological, or social condition that in the opinion of the investigator may interfere with the subject's participation in the study or evaluation of the study result.
- 4.2.20 Women who are pregnant or breastfeeding.
- **4.2.21** Prior history of thromboembolic disease, e.g., deep vein thrombosis (DVT), pulmonary emboli (PE), within 6 months of C1D1 that has required continued medical intervention.
- 4.2.22 Baseline peripheral neuropathy of Grade 2 or greater.

5.0 TREATMENT PLAN

5.1 Treatment Dosage and Administration

Telatinib will be self-administered orally twice daily. Subjects will complete a dosing diary throughout the study treatment period. Oral compliance will be determined through review of the DARF. Oral compliance for Telatinib is 50%. Less than 50% compliance is considered a deviation reportable to the IRB.

Pembrolizumab will be administered at a dose of 200mg as a 30 minute IV infusion Q3W. Effort should be made to target infusion timing to be as close to 30 minutes as possible. However, given

the variability of infusion pumps, a window of -5 minutes and +10 minutes is permitted (i.e., infusion time is 30 minutes: -5 min/+10 min).

Drug	Dose/Potency	Dose/ Frequency	Route of Administration	Regimen/ Treatment Period
Telatinib	900 mg	BID	Orally	Daily (each cycle = 3 weeks)
Pembrolizumab	200 mg	Q3W	IV infusion	Day 1 of each 3-week cycle

5.2 Toxicities and Dosing Delays/Dose Modifications

Telatinib known toxicities include:

- Nausea, vomiting, and diarrhea: Antiemetics and antidiarrheal agents may be administered to prevent or control symptoms.
- Hypertension
- Fatigue
- Liver injury
- Proteinuria/renal injury
- Hand and foot syndrome: Symptomatic therapy may be provided if necessary.
- Hypokalemia: Potassium treatment should be given in the event of hypokalemia.
- Hemorrhage
- Gastrointestinal perforation
- Cardiac function abnormality

Please refer to the telatinib IB for more details.

Toxicities may be treated symptomatically per standard of care/investigator discretion. Telatinib administration may be held at the investigator's discretion for any reason. Dose modifications are permitted. Any dose holds or modifications will be documented in the research record.

Dose Modifications and Delays for Telatinib

General dose reductions for telatinib are outlined in the following table.

Dose Level	0	-1	-2
Telatinib	900 mg BID	600 mg BID	300 mg BID
	(3 tablets twice a day)	(2 tablets twice a day)	(1 tablet twice a day)

If a dose reduction of telatinib is required and the toxicity resolves and no additional toxicities are seen after 6 weeks of treatment at the reduced dose (2 cycles), then telatinib may be increased to the dose prior to the reduction, not to exceed the original dose of 900mg (3 tablets) BID.

Any clinical event that requires dose reduction must be recorded as an AE and recorded in the CRF. For any dose that is not administered according to the protocol, the reason for the omission must be recorded in the CRF.

Suggested Dose	• Modifications	for Telatinib-	Associated Toxicities
----------------	-----------------	----------------	-----------------------

Toxicity	Non-hematologic	Hematologic
Grade 1	 Continue at the same dose level 	 Continue at the same dose level
Grade 2	• Continue at the same dose level	• Continue at the same dose level
Grade 3*	 Withhold dose until toxicity is grade ≤2, then resume treatment at the same dose level. 	 Continue at the same dose level

	 If subject experiences a second grade 3 toxicity, withhold dose until toxicity is grade <1, then reduce 1 dose level and resume treatment 	
Grade 4**	 Withhold dose until toxicity is grade ≤2, then reduce 1 dose level and resume treatment, or discontinue at the discretion of Investigator 	 Withhold dose until toxicity is grade ≤2, then reduce 1 dose level and resume treatment, or discontinue at the discretion Investigator

*Subjects who develop grade 3 fever/chills, grade 3 elevation of hepatic transaminases with ALT and AST <10X ULN, grade 3 hyperlipasemia or hyperamylasemia without clinical or other evidence of pancreatitis, grade 3 hypophosphatemia, grade 3 leukopenia, or grade 3 lymphopenia may continue telatinib without interruption at the discretion of the Investigator. NOTE: Refer to CTCAE v 5.0 for grade definitions.

**Subjects with grade 3 or 4 allergic reactions to telatinib should be removed from treatment. Subjects with grade 2 allergic reactions should be carefully assessed for potential risk of serious or life-threatening reactions following re-exposure to telatinib.

Pembrolizumab

Pembrolizumab toxicities and dosing delays/dose modifications will be managed per standard of care, the package insert, and investigator discretion. Pembrolizumab is associated with immune-related adverse events and infusion reactions. Please refer to the package insert for more details.

In the event that pembrolizumab is discontinued, treatment with telatinib may continue.

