5.3 Treatment Duration and Confirmation of Progression

Subjects will continue treatment until disease progression, intolerable toxicities, or withdrawal of consent.

In patients with initial disease progression substantiated by radiographic imaging per RECIST 1.1, study treatment may continue until repeat imaging is conducted, at least 4 weeks and no later than 8 weeks later, under the following conditions:

- No worsening of ECOG Performance Status
- No clinically relevant increases in disease-related symptoms thought to be associated with disease progression
- No requirement for intensified management of disease-related symptoms exists, including increased analgesia, radiotherapy, or other palliative care.

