6.5 Removal of Subjects from Study

Patients can be taken off the study treatment and/or study at any time at their own request, or they may be withdrawn at the discretion of the investigator for safety, behavioral or administrative reasons. The reason(s) for discontinuation will be documented and may include:

- 6.5.1 Patient voluntarily withdraws (follow-up permitted);
- 6.5.2 Patient withdraws consent (termination of treatment and follow-up);
- 6.5.3 Patient is unable to comply with protocol requirements;
- 6.5.4 Patient demonstrates disease progression (unless continued treatment with study drug is deemed appropriate at the discretion of the investigator);
- 6.5.5 Patient experiences toxicity that makes continuation in the protocol unsafe;
- 6.5.6 Treating physician determines continuation on the study would not be in the patient's best interest;
- 6.5.7 Patient becomes pregnant (pregnancy to be reported along same timelines as a serious adverse event);
- 6.5.8 Development of second malignancy (except for basal cell carcinoma or squamous cell carcinoma of the skin) that requires treatment, which would interfere with this study;
- 6.5.9 Lost to follow-up. If a research subject cannot be located to document survival after a period of 1 year, the subject may be considered "lost to follow-up." All attempts to contact the subject during the one year must be documented. This will be reviewed during an interim data monitoring visit.

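### In the suggested telatinib dose-modification table, a grade 4 non-hematologic event that is not discontinued has a looser restart threshold (grade ≤2) than a second grade 3 event (grade <1) for the same one-level reduction

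*Combined protocol and SAP*

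**What the plan says.** All of this is in the combined protocol and SAP.

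Section 5.2 sets three telatinib dose levels (900, 600 and 300 mg BID) and then gives a table of suggested modifications by grade. The non-hematologic column reads as follows:

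- **First grade 3 event:** hold until grade ≤2, then restart at the same dose.
- **Second grade 3 event:** "withhold dose until toxicity is grade <1, then reduce 1 dose level and resume treatment".
- **Grade 4 event:** "Withhold dose until toxicity is grade ≤2, then reduce 1 dose level and resume treatment, or discontinue at the discretion of Investigator".

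One footnote lets the investigator continue telatinib through certain listed grade 3 events. The other removes patients with grade 3 or 4 allergic reactions from treatment. Neither changes the recovery threshold for other grade 4 events.

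Other provisions bear on the point:

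- Section 5.2 lets the investigator interrupt telatinib for any reason and permits dose changes. Under its list of known toxicities it adds "Please refer to the telatinib IB for more details".
- Going back up to the dose used before a reduction requires the toxicity to have resolved and that "no additional toxicities are seen after 6 weeks of treatment at the reduced dose (2 cycles").
- Section 5.3 states "Subjects will continue treatment until disease progression, intolerable toxicities, or withdrawal of consent".
- Section 6.5.5 gives as a reason for removal "Patient experiences toxicity that makes continuation in the protocol unsafe". Section 6.5.6 covers the case where the physician judges that staying on study is not in the patient's best interest.

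**The concern.** One would expect the recovery required before restart to be at least as complete after a worse event. Here two entries end in the same action, one dose level down, and the entry for the more severe event accepts more residual toxicity.

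At stake is patient safety at the moment of restart. The grade 4 cell covers the most severe non-hematologic toxicities short of death. Allergic reaction is the only event type that section 5.2 itself takes out of that cell. The cell therefore also covers listed toxicities such as hemorrhage and "Gastrointestinal perforation", unless the investigator's brochure says otherwise. The formal safety stopping rule (sections 5.2.1 and 9.4) counts only first-cycle events, so a problem on restart in a later cycle would not feed it. General adverse event reporting and committee oversight would still apply.

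**Working it through.** The plan gives no figure to reproduce here. The check sets the entries side by side.

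**Inputs (section 5.2).** Dose levels: 900, 600 and 300 mg BID. Recovery thresholds, non-hematologic: ≤2 (first grade 3), <1 (second grade 3), ≤2 (grade 4).

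**Step 1. Is restart one level down open, by residual grade?**

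| Residual grade | Grade 4 entry (≤2) | Second grade 3, as printed (<1) | Second grade 3, if ≤1 was meant |
|---|---|---|---|
| 0 | yes | yes | yes |
| 1 | yes | no | yes |
| 2 | yes | no | no |
| 3 | no | no | no |

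The grade 4 entry differs from the second grade 3 entry at 2 of 4 residual grades as printed (1 and 2), and at 1 of 4 (grade 2) if ≤1 was meant. It is the looser entry wherever they differ, so the order is inverted on either reading.

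**Step 2. What dose does this mean at residual grade 2?**

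- Starting dose: 2 × 900 = 1,800 mg/day.
- Event at 900 mg BID: the grade 4 entry allows 600 mg BID, 2 × 600 = 1,200 mg/day; 1,200/1,800 = 67% of the starting dose. The second grade 3 entry keeps the dose at 0.
- Event at 600 mg BID: the grade 4 entry allows 300 mg BID, 2 × 300 = 600 mg/day; 600/1,800 = 33%. The second grade 3 entry keeps the dose at 0.
- Event at 300 mg BID: the table has no lower level, so the comparison stops there.

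**Step 3. Would a stricter rule for recurrence explain the order?** Follow the possible sequences:

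| Sequence | Recovery before restart, 1st event | Recovery before restart, 2nd event |
|---|---|---|
| Grade 3, then grade 3 | ≤2 | <1 |
| Grade 3, then grade 4 | ≤2 | ≤2, or discontinue |
| Grade 4, then grade 4 | ≤2, or discontinue | ≤2, or discontinue |

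If recurrence were the reason, the second event in the lower two rows should carry the stricter threshold as well. It does not: the strict line is written only for a second grade 3 event.

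**Step 4. Does any other text settle it?** The footnotes do not. Sections 5.3, 6.5.5 and 6.5.6 govern stopping and removal, and set no level of recovery for those who restart. The re-escalation rule applies later, once the patient is on the reduced dose. The summary of changes (section 12.7) lists no change to section 5.2.

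**The case against.** The strongest reply is that severity and recurrence are different triggers. By the time the second grade 3 line applies, recovery to ≤2 followed by the same dose has already failed once, so asking for more recovery is ordinary escalation. The grade 4 cell instead cuts the dose at once and prints an option to discontinue that the second grade 3 line lacks. The table also accepts residual grade 2 elsewhere: grade 2 toxicity is treated through, and ≤2 is the threshold after a first grade 3 event and after a grade 4 hematologic event. On that view <1 is the odd entry, and it may stand for ≤1.

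Part of this stands. A stricter rule on recurrence is reasonable, ≤2 is coherent taken alone, and the gap is one grade wide if ≤1 was meant. It does not account for the grade 3 then grade 4 sequence, where the patient has both recurrence and greater severity and still gets the looser threshold.

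The second reply is discretion. The table is only suggested, and an investigator may hold to grade 1 or 0 after a grade 4 event without departing from the protocol. That is correct and limits the practical effect. Permission to be cautious is not a recovery threshold, though, and the printed table still points the other way.

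A reader might go further and infer that the protocol directs patients back onto telatinib after, say, a grade 4 perforation with residual grade 2 toxicity. The documents do not support that. Discontinuation is printed in the same cell, sections 5.3 and 6.5 provide for stopping, and the brochure, which was not available for this review, may give event-specific guidance.

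**Conclusion.** The inconsistency is real and unexplained: for the same one-level reduction, the suggested threshold after a grade 4 non-hematologic event is looser than after a second grade 3 event. The difference covers residual grades 1 and 2 as printed, or grade 2 alone if ≤1 was intended. It matters only when the investigator restarts after a non-allergic grade 4 event, and only for the restart at the reduced dose.

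This is a cheap improvement for patient safety. The documents give no frequency for such events and show no harm or variation in practice, so none is claimed. It should not be read as a flaw in the statistical design: no sample size, power or stopping-rule figure changes. Nor is it shown that the order is a mistake. It may be intended, but then the reason is missing. The conclusion assumes that the brochure does not already set a stricter restart rule after grade 4 events.

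**What to change.** First confirm, against the source table and the telatinib brochure, whether the second grade 3 threshold is <1 or ≤1. Then replace ≤2 in the grade 4 non-hematologic cell with that same threshold, and keep the option to discontinue. Leave the second grade 3 line as strict as it is. Writing ≤1 into both cells is safe only if ≤1 is confirmed as the intended grade 3 threshold. If <1 is literal, that edit would newly allow restart at residual grade 1 after a second grade 3 event. If the present order is deliberate, one sentence under the table giving the reason would do instead.

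The cost is one cell in the next amendment, with no new visits, procedures or patients. The downside is a longer hold for some patients after a grade 4 event. If <1 is literal, a patient whose toxicity settles at grade 1 could not restart under the suggested rule.

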5.2.1 Treatment-Related Serious Adverse Events

Non-hematologic serious adverse events, graded 3 or 4 per CTCAE v5, deemed probably related or related to telatinib (alone or in combination), occurring within the first cycle of treatment, will be monitored throughout the study for safety stopping rules (see Section 9.4). Serious adverse events deemed probably related or related to Keytruda alone will not count toward safety stopping rules.

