7.1.2 Serious Adverse Events (SAE)

An adverse event is considered "serious" if, in the view of either the investigator or sponsor, it results in any of the following outcomes:

- Death.
- A life-threatening adverse event.
- In-patient hospitalization or prolongation of existing hospitalization.
- A persistent or significant incapacity or substantial disruption of the ability to conduct normal life functions
- A congenital anomaly/birth defect.
- Important medical events that may not result in death, be life-threatening, or require hospitalization may be considered serious when, based upon appropriate medical judgment, they may jeopardize the patient or subject and may require medical or surgical intervention to prevent one of the outcomes listed in this definition. Examples of such medical events include allergic bronchospasm requiring intensive treatment in an emergency room or at home, blood dyscrasias or convulsions that do not result in inpatient hospitalization, or the development of drug dependency or drug abuse.

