7.3 Safety Reporting Requirements

7.3.1.1 Reporting to the Principal Investigator

The Principal Investigator must be notified by study staff or co-investigators within 24 hours of learning of any serious adverse events, regardless of attribution, occurring during the study or within 30 days of the last administration of the study drug or until initiation of a new anticancer therapy (whichever occurs first).

Contact for Expedited Reporting:

[name], MPH [contact]; [contact]

Alternate Contact for Expedited Reporting:

[name] [contact]; [contact]

7.3.1.2 Reporting to DSMC:

Serious Adverse Events deemed to be related to the protocol and on-study deaths, including death of a research subject unless the death is expected (e.g. due to disease progression) are to be reported to the DSMC within 24 hours of awareness. Hardcopies or electronic versions of the MedWatch Form 3500A (Mandatory Reporting) or a narrative report, along with any other supporting documentation available, should be submitted to the DSMC Coordinator. The DSMC Coordinator will forward the information to the DSMC Chair, and/or medical monitor. The DSMC Chair will review all documentation upon receipt from the DSMC Coordinator and determination of whether the following actions are required: 1) takes action immediately, 2) convenes a special DSMC session (physical or electronic), or 3) defers the action until a regularly scheduled DSMC meeting. Reports to be emailed to the DSMC team at [contact].

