7.3.1.4 Reporting to the Food and Drug Administration

The sponsor-investigator of the IND, or designee must submit all reported SUSARs to the FDA on FDA Form 3500A (MedWatch).

The sponsor-investigator of the IND must notify the FDA as soon as possible but no later than:

- 7 calendar days after the sponsor-investigator's initial receipt of the information in a written IND safety report of any fatal or life-threatening SUSARs.
- **15 calendar days** after the sponsor-investigator's initial receipt of the information in a written IND safety report of any **non-fatal / non-life-threatening SUSARs**.

Copies of IND Safety Reports will be kept in the Trial Master File in the SOCCI CCTO.

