9.4 Stopping Rules

Let P_T be the true probability that a patient experiences a treatment-related SAE (as defined in Section 5.2.1) within the first cycle of treatment in the AGC cohort. The trial will stop if there is statistical evidence that P_T exceeds 30%. We will use a Bayesian sequential design by checking whether P_T exceeds this threshold value after 6, 15, and 21 patients are evaluable for SAEs. The decision rule is to stop the trial if the posterior probability that P_T exceeds 0.30 is 0.97 or more; $P(P_T > 0.3 | data) > 0.97$. A noninformative prior distribution for P_T will be used.

Table 1 gives the stopping rules for the design at each look and column 2 gives the maximum number of patients with treatment-related SAEs in order for the trial to proceed. For example, if 4 or more treatment-related SAEs are observed after enrolling 6 patients, the trial stops. The third column gives the probability of stopping the trial when in fact, the true $P_T = 0.30$. This is the equivalent of the Bayesian type I error probability. The target type I error probability was set at 0.10.

Number of Patients	Number to Continue	Probability to Stop	Cumulative Probability to Stop
6	3	0.070	0.070
15	7	0.028	0.098
21	10	0.006	0.104

Table 1. Stopping rules based on three interim looks. Number to continue is the maximum number of treatment-related SAEs for not stopping the trial.

Table 2 gives the design operating characteristics under selected values of the true probability P_{T} . It gives the probability of stopping the trial under the alternative hypothesis, the expected sample size, and the average sample size given that the trial stopped. For example, if the true value of P_{T} is 0.5, then there is an 63.6% chance that the trial is stopped early, and the average sample size is about 14.5. On the other hand, there is a small chance of stopping the trial if P_{T} is small; 1.9% chance of stopping the trial when in fact $P_{T} = 0.2$.

	True Value	Probability to	Expected	Expected
	of P ⊤	Stop	N	N given that we Stopped

IIT2020-11-[name]-TELAT

0.20	0.0197	20.73	7.3	
0.30	0.1043	19.78	9.2	
0.40	0.3212	17.66	10.6	
0.50	0.6362	14.50	10.8	

Table 2. Design operating characteristics under different scenarios for the true probability of toxicity P_{T} .

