Similar stopping rules are used for the HCC cohort with a target probability of treatment-related SAEs not to ne exceeded equal to 0.3. Tables 3 and 4 present the operating characteristics of this stopping rules for HCC arm.

Number of Patients	Number to Continue	Probability to Stop	Cumulative Probability to Stop
6	3	0.070	0.070
15	7	0.028	0.098
24	11	0.010	0.108

Table 3. Stopping rules based on three interim looks. Number to continue is the maximum number of treatment-related SAEs for not stopping the trial.

True Value	Probability to	Expected	Expected
of P ⊤	Stop	N	N given that we Stopped
0.20	0.0198	23.67	7.46
0.30	0.1087	22.48	10.03
0.40	0.3480	19.79	11.90
0.50	0.6866	15.79	12.05

Table 4. Design operating characteristics under different scenarios for the true probability of toxicity P_{T} .

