10.5.2 Safety Monitoring

High Risk Monitoring

Oversight of the progress and safety of the study will be provided by the PI. The PI will maintain continuous safety monitoring for the duration of the study by reviewing subject/study data. Adverse events and unanticipated problems are not expected, but if they occur, they will be documented and reported according to CS-IRB policies and procedures. If the PI becomes aware of any new safety information that may place subjects at increased risk than what was previously known, the IRB will be promptly notified and if warranted, enrollment may be held until the PI determines whether a modification to the study is necessary and/or the informed consent documents are updated accordingly. It is the responsibility of the principal investigator to adhere to the Data Safety Monitoring Plan throughout the life of the study.

In addition, this protocol will utilize the SOCCI Data and Safety Monitoring Committee to provide another layer of data and safety oversight. DSMC membership and responsibilities are governed by the committee charter. Every three (3) months the DSMC findings and recommendations will be reported in writing to the Principal Investigator as a summary letter which will be forwarded by the Principal Investigator or designee to the CS-IRB. The DSMC may increase or decrease the frequency of study review, at their discretion. Refer to the DSMC Charter for details of the DSMC review.

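### The safety stopping rule counts only grade 3 or 4 SAEs, so a telatinib-related cycle 1 SAE recorded only as fatal (grade 5) does not enter the count in either cohort

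*Combined protocol and SAP*

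**What the plan says.** Section 5.2.1 names the events monitored for the stopping rule: "Non-hematologic serious adverse events, graded 3 or 4 per CTCAE v5, deemed probably related or related to telatinib (alone or in combination"), occurring in the first cycle. SAEs attributed to Keytruda alone are left out.

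Section 9.4 takes its event from there. P_T in the AGC cohort is the probability that "a patient experiences a treatment-related SAE (as defined in Section 5.2.1) within the first cycle of treatment". The limit is 30%, the posterior cut-off is 0.97 and the prior is described only as noninformative. The looks are at 6, 15 and 21 patients, with at most 3, 7 and 10 affected patients to continue. The worked example reads: "if 4 or more treatment-related SAEs are observed after enrolling 6 patients, the trial stops". For the other cohort, "Similar stopping rules are used for the HCC cohort", with looks at 6, 15 and 24, at most 3, 7 and 11 to continue, and no separate event definition.

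The general SAE definition in Section 7.1.2 covers an event if "it results in any of the following outcomes", and death heads that list. No section extends the stopping-rule count to grade 5 or fatal events.

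Fatal events are handled elsewhere:
- Section 7.3.1.2 sends "Serious Adverse Events deemed to be related to the protocol and on-study deaths" to the DSMC within 24 hours, except deaths that are expected.
- Section 7.3.1.4 gives 7 calendar days for reporting "any fatal or life-threatening SUSARs" to FDA.
- Section 10.5.2 says that on new safety information "enrollment may be held until the PI determines whether a modification to the study is necessary".

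**The concern.** The count ranks outcomes the wrong way round. A related grade 3 SAE in cycle 1 moves the trial towards stopping; a related death recorded only as grade 5 does not. The documents give no reason for this. It is an omission from the counted event, not a contradiction between sections.

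The case can arise. Section 5.2 lists hemorrhage, gastrointestinal perforation, liver injury and cardiac function abnormality among the known telatinib toxicities. Section 7.2.1 asks for a toxicity grade but does not say how to grade an event that worsens to death, so a single grade 5 record is possible.

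Section 9.3.3 rules out interim analyses for futility or efficacy, so Section 9.4 is the trial's only pre-specified stopping boundary. Near that boundary, the written rule can return a formal decision to continue where the same events with the death counted would stop the trial. The decision would then rest on discretion.

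**Working it through.** **Inputs.** Limit 0.30, cut-off 0.97, and looks and boundaries as in Section 9.4, Tables 1 and 3. The prior parameters are not given; Beta(1,1) is assumed.

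**1. Boundaries.** With x affected patients among n, the posterior probability is 1 − F(0.30), where F is the Beta(1 + x, 1 + n − x) distribution function.

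| Look | One below boundary: continue | At boundary: stop |
|---|---|---|
| 6, both cohorts | 3/6: 0.874 | 4/6: 0.971 |
| 15, both cohorts | 7/15: 0.926 | 8/15: 0.974 |
| 21, AGC | 10/21: 0.961 | 11/21: 0.986 |
| 24, HCC | 11/24: 0.956 | 12/24: 0.983 |

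The uniform prior reproduces every printed boundary. A Beta(0.5, 0.5) prior does not: it gives 0.9699 at 4/6, just under 0.97.

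**2. The plan's operating characteristics.** At the first look with P_T = 0.30:

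P(X ≥ 4 of 6) = 15(0.3⁴)(0.7²) + 6(0.3⁵)(0.7) + 0.3⁶ = 0.0595 + 0.0102 + 0.0007 = 0.0705 (Tables 1 and 3 print 0.070).

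An exact binomial recursion, carrying forward only the paths that have not stopped, gives the overall probability of stopping:

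| P_T | AGC (3/7/10) | HCC (3/7/11) |
|---|---|---|
| 0.20 | 0.0197 | 0.0198 |
| 0.30 | 0.1043 | 0.1087 |
| 0.40 | 0.3212 | 0.3480 |
| 0.50 | 0.6362 | 0.6866 |

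These match Tables 2 and 4. The tables are correct as functions of P_T; the question is which patients P_T includes.

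**3. One uncounted death.** Each row of the first table is also a pair of readings of the same data. With three grade 3-4 patients and one fatal-only patient among six, the written rule sees 3/6 and continues; with the death counted it is 4/6 and the trial stops. The same reversal occurs at 15, 21 and 24.

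The effect is confined to the boundary. One, two or three related deaths among six with no other counted event give a decision to continue either way, since even 3/6 is below 0.97.

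**4. Effect on the chance of stopping.** The documents give no grade 5 rate, so this step is an assumption with a range. Let f be the share of affected patients who have only a grade 5 record. The counted rate is then (true grade 3-5 rate) × (1 − f).

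| True rate | f | Counted rate | AGC | HCC |
|---|---|---|---|---|
| 0.50 | 0 | 0.500 | 0.636 | 0.687 |
| 0.50 | 0.05 | 0.475 | 0.557 | 0.604 |
| 0.50 | 0.10 | 0.450 | 0.476 | 0.517 |
| 0.50 | 0.20 | 0.400 | 0.321 | 0.348 |
| 0.40 | 0 | 0.400 | 0.321 | 0.348 |
| 0.40 | 0.05 | 0.380 | 0.266 | 0.287 |
| 0.40 | 0.10 | 0.360 | 0.217 | 0.232 |
| 0.40 | 0.20 | 0.320 | 0.136 | 0.143 |

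**5. First two looks only.** The last look falls at full enrollment. Over the looks at 6 and 15 alone, which are the same in both cohorts, the chance of stopping at a true rate of 0.50 is 0.568 with f = 0, 0.495 with f = 0.05 and 0.423 with f = 0.10.

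**The case against.** The strongest reply is that a related death would not pass unseen. Reporting related SAEs to the DSMC within 24 hours is mandatory, and the DSMC Chair must review the documents and choose among set actions, including immediate action. Section 7.3.1.3 adds IRB notification within 10 business days for unanticipated, possibly related events. Case-level review protects better against deaths than a tally that weighs a death like a grade 3 event. This stands as a limit on the consequence. What follows the review is still a judgement without a numerical boundary, and it does not alter the count.

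Second, the looks at 21 and 24 come after the last planned patient, and Section 4.0 names enrollment looks only after the 6th and 15th. A reversal at the last look spares no new patient a first dose, although it can affect ongoing treatment and the formal safety conclusion. This also stands; step 5 of the working gives the figures without that look.

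Third, the upper end of the assumed range is extreme. A rate of 0.50 with f = 0.20 means that 0.50 × 0.20 = 10% of patients have a fatal-only related event in cycle 1, about 2.1 of 21 in AGC. The resulting figure describes the boundary alone, not all oversight.

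Fourth, a patient with a separately recorded grade 3-4 related SAE before death already counts. That is true, but it depends on recording practice that the protocol does not fix.

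**Conclusion.** The concern holds and should be fixed. As written, the count in both cohorts leaves out a telatinib-related cycle 1 SAE recorded only at grade 5. One such patient can turn a decision to stop into a decision to continue at any look. The boundary calculation rests on a uniform prior, which the protocol does not name but which reproduces its boundaries. The loss in stopping probability rests on an assumed fatal-only share. At a true rate of 0.40, for example, a 5% share lowers it from 0.321 to 0.266 (AGC) and from 0.348 to 0.287 (HCC).

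The defect is in the formal tally, not in all safety oversight, and no printed number is wrong. That grade 5 is the fatal grade comes from the CTCAE v5 scale that the protocol adopts; the restriction to grades 3 and 4 excludes any other grade in any case.

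**What to change.** In Section 5.2.1, replace the restriction to grades 3 and 4 with *grade 3 or higher, including grade 5 (fatal)*, so that the event used in Section 9.4 takes in the death outcome listed in Section 7.1.2. Keep the non-hematologic scope, the attribution requirement and the cycle 1 window. State that each patient counts once, at the worst grade.

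Fatal hematologic SAEs and deaths rated only as possibly related would remain outside the count and would depend on DSMC and PI review. The protocol should say whether that is intended. If leaving grade 5 out was itself deliberate, the protocol should say so and give the reason.

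The cost is a short amendment to Section 5.2.1 with IRB approval. The 30% limit, the boundaries 3/7/10 and 3/7/11 and Tables 1-4 can stay as they are, because they depend only on P_T. No new data are needed.
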